7.4. Missing data

The occurrence of missing data in TONIC trial is expected to be low and, when present, is expected to be equally distributed across the 3 treatment groups. We estimate that careful selection of patients during the 16 weeks screening phase and the consent process should result in no more than 10% missing data from patients who drop out before completing the 96 week treatment period. In primary, intention-to-treat analyses, patients with missing data will be considered unimproved on the primary outcome measure.

The proportions with missing data will be compared across treatment groups using χ^2 tests. If the amount of missing data exceeds 10% and the frequency of missing data differs by treatment group, then a variety of sensitivity analyses will be carried out to compare with the primary analysis using all available non-missing data: (1) compare pessimistic and optimistic imputations of the missing values, (2) correct for missing data using multiple imputation with 10 replicated samples, and (3) use mixed random effects logistic or linear regression models, depending on the type of outcome measure.

7.5. Justification of sample size

The planned sample size for the TONIC trial is 180 patients with equal allocation to each of the three treatment groups (60 per group).

We based the sample size estimates on a two-group, binomial comparison of the proportions of patients satisfying the primary outcome, reduction in serum ALT to either 50% of the baseline value OR to 40 U/L or lower which is sustained for at least one year (defined in Section 7.2) over the 96 week course of treatment. Since TONIC is a three group trial with two primary hypotheses, we assume that the two primary comparisons, metformin vs. placebo and vitamin E vs. placebo, require the same sample size and reduce the type I error from 0.05 to 0.025 (Bonferroni correction). Expected proportions improved were approximated using pilot data from a 48-week metformin study ([name], personal communication) and from a consensus among our investigators as to the response in the placebo group. Currently, there are no available data to estimate the response in vitamin E, which is assumed, for purposes of planning the trial, to be the same as for metformin.

The sample size calculations were performed using the PS⁴⁵ software using the formula:

$$n = \frac{\left[z_{1-\alpha/2} \sqrt{2\bar{\pi}(1-\bar{\pi})} + z_{1-\beta} \sqrt{\pi_1(1-\pi_1) + \pi_2(1-\pi_2)} \right]^2}{(\pi_1 - \pi_2)^2}$$

where,

n = sample size per group

π_1 = expected proportion improved in placebo group (assumed=0.20)

π_2 = expected proportion improved in metformin or vitamin E group (0.50)

$\bar{\pi}$ = average of π_1 and π_2

α = Two-sided type I error (0.025, Bonferroni corrected for two comparisons)

β = Type II error (0.10; ie, 90% power)

The number per group, using the above formula is 60 patients; or a total of 180 for the trial. As indicated in Section 7.4, patients with missing primary outcome data will be considered unimproved and will be included in the 180 patients.

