8.	Human subject issues.....	45
8.1.	Overview.....	45
8.2.	Institutional Review Board approval.....	45
8.3.	Informed consent.....	45
8.4.	Patient confidentiality.....	45
9.	References.....	46

TONIC Trial Protocol

10. Appendices.	50
10.1. Participating centers.. . . .	51
10.2. Committees.	52
10.3. Data collection schedule.	53
10.4. Whole blood draw schedule.. . . .	54
10.5. Glossary.	55
10.6. Document history.. . . .	56

TONIC Trial Protocol

Design synopsis

Title

- Treatment of Nonalcoholic Fatty Liver Disease in Children (TONIC)

Sponsor

- NIDDK and NICHD

Objective

- To determine whether 96 weeks of treatment with either metformin or vitamin E leads to sustained reduction in serum ALT in nondiabetic children with NAFLD compared to treatment with placebo

Type of study

- Phase III randomized clinical trial
- Multicenter, masked, placebo-controlled

Treatment groups

- Group 1: Metformin, 500 mg PO b.i.d. and vitamin E-placebo b.i.d.
- Group 2: Vitamin E, 400 IU natural form PO b.i.d. and metformin-placebo b.i.d.
- Group 3: Metformin-placebo b.i.d. and vitamin E-placebo b.i.d.

Population

- Children with NAFLD aged 8-17 years at first screening visit

Study duration – per patient

- Up to 16 weeks (112 days) of screening prior to randomization, including at least 3 months of drug washout for those using antiNAFLD or antidiabetic medications prior to randomization
- 96-week treatment
- 24-week post-treatment follow-up

Study duration – per calendar time

- Recruitment phase: August 2005 - September 30, 2007
- Follow-up phase: August 2005 - October 2009

TONIC Trial Protocol

Design synopsis

Sample size justification

- Total of 180 patients in 3 groups of equal size (60 per group)
- Primary comparisons
 - Metformin vs placebo
 - Vitamin E vs placebo
- Error protection
 - Type I = 0.025 (0.05, Bonferroni protected)
 - Type II = 0.10 (90% power)
- Effect size for sustained reduction in ALT after 96 weeks of treatment
 - Expected percent with sustained reduction in the placebo group: 20%
 - Expected percent with sustained reduction in the metformin or vitamin E groups: 50%
- Statistical test and sample size software
 - Chi-squared test for two proportions
 - Dupont and Plummer PS software
- Source of data for response rates
 - Open-label pilot studies of metformin and vitamin E at the UCSD NASH CRN clinic
 - Consensus of NASH CRN clinicians regarding expected response in the placebo group

Number of clinical centers

- 8

Inclusion criteria

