7.3. Statistical analysis

Primary hypotheses:

Statistical analyses for the two primary hypotheses will follow the intention-to-treat paradigm, which means that all randomized patients with baseline and 96 week serum ALT values will be analyzed in the treatment group to which they were assigned. Any randomized patient who does not have the requisite ALT values will be accounted for and compared by assigned treatment group. Patients not able to be included in the intention-to-treat analyses will be compared to those who are included with respect to demographic and other characteristics.

Since the primary outcome measure, defined in Section 7.2, is a binary indicator of sustained reduction in ALT after 96 weeks of treatment compared to baseline and since the randomization is stratified by clinic, P-values for the primary hypotheses will be derived from the Mantel-Haenszel χ^2 test for stratified 2x2 tables⁴⁴. Two P-values will be derived: one comparing proportions improved in the group assigned to metformin compared to the group assigned to placebo and another comparing the group assigned to vitamin E to the group assigned to placebo. Since two primary comparisons are planned, a P-value of 0.025 will be considered significant, applying a Bonferroni correction for multiple comparisons.

Given the randomized design and adequate size planned for the TONIC trial, it is unlikely that confounding of the treatment groups by covariates related to the change in serum ALT will occur. However, if confounding should occur, logistic regression analyses with sustained reduction in ALT as the binary response and treatment group indicators and any suspected confounders as covariates will be carried out to determine the sensitivity of the primary P-values to confounding.

Secondary hypotheses:

Statistical analyses for the first secondary hypothesis, that treatment with metformin or vitamin E will result in sustained reduction in serum AST and GGT compared to treatment with placebo, will be the same as described for primary hypotheses.

The second secondary hypothesis, that metformin and vitamin E are equally effective in achieving histologic improvement in nondiabetic children with NAFLD, involves the histologic outcome measure. Equivalence will be assessed by means of 95% confidence intervals on the difference in proportions improved.

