7.6. Interim analysis

An independent Data and Safety Monitoring Board (DSMB), appointed by the NIDDK, is responsible for approving the protocol for the TONIC trial and for monitoring the accumulating interim data as the trial progresses to ensure patient safety and to review efficacy. The DSMB is a multidisciplinary group with a written charge provided by the NIDDK. The DSMB reports to the NIDDK, which will, in turn, communicate DSMB recommendations to the investigators, as appropriate. The DSMB meets in person to approve the protocol. After the trial commences, the DSMB meets twice a year to review data or other issues – once in person and once by telephone conference. The DSMB may request more frequent meetings if necessary to fulfill its charge. It may also request additional safety reports on a more frequent basis. For example, all serious adverse events are reported to the DSMB for their consideration and recommendations as they occur.

Interim data on safety measures requested by the DSMB are reviewed at each of the scheduled semi-annual full meetings. Two additional written safety reports will be reviewed by the DSMB between scheduled full meetings. Serious adverse events will be reviewed by the DSMB as they occur (as close to real time as possible) with the option of a teleconference discussion if any DSMB member so requests.

The DSMB will review quarterly reports by masked treatment groups of incident hepatotoxicities, as well as counts of patients who required more frequent liver function testing due to rises in ALT levels of more than 2 times baseline ALT or beyond 300 U/L. The DSMB will also examine the trends in ALT or AST levels for each patient who experiences a rise in ALT.

The DSMB reviews one planned interim analysis of the primary outcome measure. O'Brien-Fleming statistical stopping guidelines for efficacy apply. This interim efficacy analysis will occur when approximately 50% of the data are complete or when approximately 90 of the 180 patients have completed the 96 week course of treatment.

The DSMB also reviews the overall progress of the trial in terms of recruitment and data quality and makes a formal recommendation to the NIDDK at the end of each scheduled meeting as to whether the trial should continue unmodified, continue with protocol modifications, or be stopped.

TONIC Trial Protocol

8. Human subject issues

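### The stated 90% power at 60 per group holds only with no missing outcomes; with missing counted as unimproved it falls to about 84% at the plan's 10% ceiling, unless the planning rates already allow for this

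*Supplement*

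**What the plan says.** Section 7.5 sizes each primary comparison (metformin v placebo, vitamin E v placebo) with a two-proportion formula. Its inputs are 20% improved on placebo, 50% on active treatment, two-sided 0.025 after Bonferroni, and 90% power. It arrives at 60 per group, 180 in all. The synopsis repeats the 0.10 type II error. The active rate is attributed to a 48-week metformin pilot and the placebo rate to investigator consensus; vitamin E is assumed to match metformin.

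On missing outcomes, Section 7.5 ends: "As indicated in Section 7.4, patients with missing primary outcome data will be considered unimproved and will be included in the 180 patients". Section 7.4 applies the same rule to the primary outcome. It expects missing data to be low and equal across groups, and says that careful selection and consent "should result in no more than 10% missing data from patients who drop out before completing the 96 week treatment period". Section 7.3 describes the intention-to-treat set differently, as randomized patients who have baseline and week 96 ALT.

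On error control, Section 7.3 says: "Since two primary comparisons are planned, a P-value of 0.025 will be considered significant". Section 7.6 plans one interim efficacy analysis when about 90 of 180 patients have completed treatment, and says that O'Brien-Fleming "statistical stopping guidelines for efficacy apply". No interim or final critical value is given.

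**The concern.** A patient counted as unimproved stays in the denominator and cannot be a success, so missing outcomes shrink both response rates and the gap between them. Keeping such patients inside the 180 therefore does not make the sample size robust to dropout. The calculation uses the full 20% and 50%, and the paragraph that adds the missing-data rule changes neither the rates nor the number.

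What is at stake is how a null result is read. A reader told that each comparison had 90% power will take a non-significant result as stronger evidence against a 30-point effect than the design supports if some outcomes were missing.

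A second, smaller matter is that the final threshold in Section 7.3 rests on Bonferroni alone and is not tied to the interim look in Section 7.6.

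**Working it through.** **Inputs.** From Section 7.5: rates 0.20 and 0.50, two-sided 0.025 (z = 2.2414), power 0.90 (z = 1.2816), n = 60 per group. From Section 7.4: missing at most 10%, equal across groups, counted as unimproved. From Section 7.6: one look at about half the data.

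**1. The plan's own figure.** The mean rate is 0.35.

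n = [2.2414·√(2·0.35·0.65) + 1.2816·√(0.16 + 0.25)]² / 0.30² = (1.5119 + 0.8206)² / 0.09 = 60.45

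This agrees with the stated 60 to within rounding. Solving the same formula for power at n = 60:

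Power = Φ{[0.30·√60 − 1.5119] / √0.41} = Φ(1.268) = 89.8%

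An exact calculation for the uncorrected chi-squared test gives 90.3%. The 90% is therefore right for complete data, with nothing to spare.

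**2. Missing counted as unimproved.** This step assumes that 20% and 50% apply to patients with observed outcomes. With a fraction d missing in each group, the rates become 0.20(1 − d) and 0.50(1 − d).

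At d = 0.10 the rates are 0.18 and 0.45, with mean 0.315:

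Power = Φ{[0.27·√60 − 2.2414·√(2·0.315·0.685)] / √(0.18·0.82 + 0.45·0.55)} = Φ{(2.0914 − 1.4724) / 0.6286} = Φ(0.985) = 83.8%

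| Missing | Rates | Power, plan's formula | Power, exact |
|---|---|---|---|
| 0% | 20% v 50% | 89.8% | 90.3% |
| 5% | 19% v 47.5% | 87.0% | 87.7% |
| 10% | 18% v 45% | 83.8% | 84.6% |

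For scale, 90% power at 18% v 45% would take 71.2, so 72 per group.

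**3. Missing patients left out, as Section 7.3 describes.** Ten percent missing leaves 54 per group at 20% v 50%:

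Power = Φ{[0.30·√54 − 1.5119] / √0.41} = Φ(1.082) = 86.0%

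**4. The other reading of the rates.** If 20% and 50% already count missing patients as failures at 10% missing, the rates among completers are 0.20/0.90 = 22% and 0.50/0.90 = 56%. Power at 60 is then the 89.8% of step 1.

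**5. The interim look.** A two-look O'Brien-Fleming boundary rejects if |Z| exceeds c·√2 at half the information or c at the end; the two statistics have correlation √0.5. Setting the total two-sided error to 0.025 gives c = 2.250. The interim bound is z = 3.183 (P = 0.0015) and the final bound is P = 0.0244. An O'Brien-Fleming-type spending function can give a final level near 0.0247 instead, so the exact value depends on the variant chosen.

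Using z = 2.2414 (P = 0.025) at the end, after the 3.183 look, gives 0.0256 per comparison. Twice that is 0.0511, but the two comparisons share the placebo group (correlation 0.5). The simulated familywise error is about 0.0475, against about 0.0465 with no look. Moving the final level to 0.0244 lowers fixed-sample power at 10% missing from 83.8% to 83.5%.

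**The case against.** The strongest reply is that 84% depends on a reading the plan does not state. Section 7.5 speaks of the proportion of patients expected to improve in each group and, in the same section, says that missing patients count as unimproved. One can fairly read the 20% and 50% as rates per randomized patient, with dropouts already counted as failures. On that reading 90% power stands. This much of the objection holds: a reader might infer that the design simply delivers 84%, or that its type II error is 0.16, and the documents do not support so flat a statement. Equally, nothing in Section 7.5 says that the rates are net of missing data. They are traced to a pilot study and to consensus, without mention of dropout. The document history (Section 10.6) records that missing data were once covered by a separate inflation of the sample size. That leans towards rates among observed patients, but it is superseded text and does not settle the matter.

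Second, 10% is a ceiling and Section 7.4 expects little missing data, so the result is a range.

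Third, the formula is applied correctly, and the shortfall is modest beside the uncertainty in the rates: at 60 per group, power is 72.8% for 25% v 50% and 97.7% for 15% v 50%. That is true, but it does not excuse stating a power that omits the plan's own missing-data rule.

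Fourth, recruitment and follow-up were scheduled to end before the latest version was dated, so a restated power cannot alter conduct. It can still alter how a null result is interpreted.

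On the interim look, a reader might infer that it is ignored, or that overall error exceeds 5%. Neither is supported: Section 7.6 names O'Brien-Fleming guidelines, and the shared placebo group keeps familywise error below 0.05.

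**Conclusion.** The point holds in conditional form. The sample-size arithmetic is sound for complete data, but the stated 90% makes no visible allowance for the missing outcomes that the plan expects and counts as unimproved. If 20% and 50% apply to patients with observed outcomes, and missingness is equal across groups, power is between 83.8% (10% missing) and 89.8% (none), with 87.0% at 5%. At the ceiling the type II error is about 0.16 against a stated 0.10. The analysis set described in Section 7.3 does not restore 90% either; it gives 86.0% at 10% missing. If the rates are already net of missing data, 90% stands, but the plan has to say so.

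The interim matter is minor. What is lacking is a final critical value that connects Section 7.3 with Section 7.6. The excess from keeping 0.025 is about 0.0006 per comparison, with no breach of the overall 5%.

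**What to change.** In Section 7.5 and the synopsis, do one of two things:

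- Restate power as about 84% to 90% for 10% to 0% missing outcomes counted as unimproved, and say that 90% applies only when none are missing.
- State explicitly that 20% and 50% already count missing patients as failures, which at 10% missing means about 22% and 56% among completers, and say why those figures are reasonable.

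In Section 7.3, give the final per-comparison threshold that goes with the O'Brien-Fleming look: about P<0.0244 at the end, with about P<0.0015 at the interim. Name the variant used, since it moves the value slightly.

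The cost is a few sentences and, under the first option, a less favourable power statement. Enrolment does not change. The lower final threshold costs about 0.2 points of power by the plan's formula (83.8% to 83.5% at 10% missing, before rounding).

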7.6. Interim analysis

An independent Data and Safety Monitoring Board (DSMB), appointed by the NIDDK, is responsible for approving the protocol for the TONIC trial and for monitoring the accumulating interim data as the trial progresses to ensure patient safety and to review efficacy. The DSMB is a multidisciplinary group with a written charge provided by the NIDDK. The DSMB reports to the NIDDK, which will, in turn, communicate DSMB recommendations to the investigators, as appropriate. The DSMB meets in person to approve the protocol. After the trial commences, the DSMB meets twice a year to review data or other issues – once in person and once by telephone conference. The DSMB may request more frequent meetings if necessary to fulfill its charge. It may also request additional safety reports on a more frequent basis. For example, all serious adverse events are reported to the DSMB for their consideration and recommendations as they occur.

Interim data on safety measures requested by the DSMB are reviewed at each of the scheduled semi-annual full meetings. Two additional written safety reports will be reviewed by the DSMB between scheduled full meetings. Serious adverse events will be reviewed by the DSMB as they occur (as close to real time as possible) with the option of a teleconference discussion if any DSMB member so requests.

The DSMB will review quarterly reports by masked treatment groups of incident hepatotoxicities, as well as counts of patients who required more frequent liver function testing due to rises in ALT levels of more than 2 times baseline ALT or beyond 300 U/L. The DSMB will also examine the trends in ALT or AST levels for each patient who experiences a rise in ALT.

The DSMB reviews one planned interim analysis of the primary outcome measure. O'Brien-Fleming statistical stopping guidelines for efficacy apply. This interim efficacy analysis will occur when approximately 50% of the data are complete or when approximately 90 of the 180 patients have completed the 96 week course of treatment.

The DSMB also reviews the overall progress of the trial in terms of recruitment and data quality and makes a formal recommendation to the NIDDK at the end of each scheduled meeting as to whether the trial should continue unmodified, continue with protocol modifications, or be stopped.

TONIC Trial Protocol

8. Human subject issues

8.1. Overview

The study protocol, questionnaires, and consent forms will be submitted to each participating center's IRB. Sites which recruit patients will submit their recruitment materials to their IRB prior to use. A site may not initiate any patient contact about the TONIC trial until the site has IRB approval for the trial. All study personnel must complete training in the Protection of Human Subjects per NIH guidelines. The proposed study anticipates recruiting a significant proportion of racial/ethnic minorities (African-Americans, Asian-Americans and Hispanics) as well as non-Hispanic white subjects.

8.2. Institutional Review Board approval

A site may not initiate patient activities in the TONIC trial until the site has Institutional Review Board (IRB) approval for the trial. Consent forms must have IRB approval. Sites must provide the DCC with a copy of the initial IRB approval notice and subsequent renewals as well as copies of the IRB approved consent statements.

8.3. Informed consent

A prototype consent will be prepared for the trial for screening to determine eligibility with an affirmation of consent for randomization in the trial. Individual sites may add material but may not delete material thought to be necessary for informed consent. Clinics may reformat and reword information to conform to their local requirements. The patient must sign the consent to be eligible for the trial. The consent form will describe the purpose of the trial, the procedures to be followed, and the risks and benefits of participation. Copies of the signed consent forms will be given to the patient, and this fact will be documented in the patient's record.

10.2. Committees

- Steering Committee
 - Executive Committee
 - Database Committee
 - Measures and Assessments Committee
 - Pathology Committee
 - Standards of Care Committee
 - Pediatrics Committee
 - Ancillary Studies Committee
 - Presentations and Publications Committee
 - TONIC Eligibility Committee
 - Treatment Trial Protocol Committee
 - Pilot and Feasibility Studies Committee
-

10.3. Data collection schedule

Assessment/Procedure	Screening visits			Follow-up visits									
	S1	S2	RZ	Weeks from randomization									
				4	12	24	36	48	60	72	84	96	120
Consent	X	.	X
Baseline (B) or interim (I) medical history	B	.	.	I	I	I	I	I	I	I	I	I	I
Review for adverse effects	X	.	.	X	X	X	X	X	X	X	X	X	X
Review of concomitant medications	X	.	.	X	X	X	X	X	X	X	X	X	X
AUDIT (A) or interim (I) alcohol quest	A	.	.	I	I	I	I	I	I	I	I	I	I
Study drug dispensing	.	.	X	.	X	X	X	X	X	X	X	.	.
Review of study drug adherence	.	.	.	X	X	X	X	X	X	X	X	X	.
Detailed (D) or focused (F) physical exam	D	.	.	F	F	F	F	D	F	F	F	D	D
DEXA scan for body fat	.	X	X	.
MRI for body fat (optional)	.	X	X	.
Liver biopsy (H for ≤6 months)	H	X	.
Block Brief nutrition questionnaire	.	X	X	.	.	.	X	X
Modifiable activity questionnaire	.	X	X	.	.	.	X	X
Pediatric quality of life	.	X	X	.	.	.	X	X
Liver symptom questionnaire	.	X	X	.	.	.	X	X
Labs													
Metabolic panel	X	.	.	X	X	X	X	X	X	X	X	X	X
Hematology	X	X	.	X	.	X	.	X	X
Fasting lipid profile	X	X	.	X	.	X	.	X	X
Fasting serum glucose	X	X	.	.	.	X	.	.	.
Hepatic panel	.	X	.	X	X	X	X	X	X	X	X	X	X
Vitamin B12	.	X	.	.	.	X	.	X	.	X	.	X	X
GGT, prothrombin time, HbA1c	.	X	X	.	.	.	X	X
OGTT with insulin and C-peptide	.	X	X	.	.	.	X	X
Free fatty acid, leptin, C-reactive protein	.	X	X	.	.	.	X	X
Urine pregnancy test (females)	X	X	X	X	X	X	X	X	X	X	X	X	X
Banking													
Fasting serum, plasma banking	.	X	.	.	.	X	.	X	.	X	.	X	.
Serum vitamin E (on banked specimen)	.	X	X	.	.	.	X	.
DNA for banking	.	X
Closeout form (CO)	X

Note: **Detailed (D) physical** includes measurement of height, weight, waist, hips; vital signs (temperature, heart rate, blood pressure); triceps skin fold thickness; mid-upper arm circumference; examination for scleral icterus and pedal edema and auscultation of the heart and lungs; general physical findings (hepatosplenomegaly, peripheral manifestations of liver disease, ascites, wasting, fetor); Tanner staging. **Focused (F) physical** includes measurement of height, weight; vital signs (temperature, heart rate, blood pressure); examination for scleral icterus and pedal edema and auscultation of heart and lungs.

OGTT: Blood samples will obtained only at baseline and at 2 hours after administration of glucose solution.

Lipid profile: total cholesterol, triglyceride, LDL, HDL.

Hematology: Hemoglobin, hematocrit, WBC, platelet count.

Metabolic panel: sodium, potassium, chloride, bicarbonate, calcium, phosphate, BUN, creatinine, uric acid, albumin, total protein.

Hepatic panel: total bilirubin, direct bilirubin, AST, ALT, alkaline phosphatase.

Fasting visits: All visits except RZ.

TONIC Trial Protocol

10. Appendices

